## **9.2 Garmin wearable devices**

Eligible participants will be provided with wearable devices (Garmin Vivosmart4) to measure heart rate, oxygen saturation, step count and sleep quality. Aparito has a partnership with Garmin which allows the hardware sensor data to be communicated directly to the Atom5™ platform and does not therefore need to interact with the Garmin software (Garmin Connect). Participants will be asked to wear the devices continuously for four consecutive weeks (except when recharging the devices), when they first receive the device, at 6 months and then at 12 months. During each week of use, participants will be prompted to undertake a 40-step test, which will involve participants being asked to walk 40 steps as an exertional test to assess for changes in heart rate and oxygen saturation before and after the test.

## **9.3 Laboratory Data**

Once analysed, blood sample and saliva data will be inputted directly into the Atom5™ platform by researchers within the laboratory. Laboratory staff will have no access to patient identifiable data and will input results using the participant's unique Global ID.

## **9.4 Co-production**

Co-production workshops will be audio recorded using an encrypted digital recorder. Participants will also complete a short demographic questionnaire and field notes will be taken, as necessary.

Recordings will be transcribed verbatim by a professional transcription service who is approved by the University of Birmingham and will sign a confidentiality agreement. The transcription company will delete the recording once the researcher is happy with the accuracy of the transcript. The transcripts will be anonymised and assigned a unique identification number.

## **9.5 Data storage**

### **9.5.1 Aparito Atom5™**

Data collected from questionnaires, wearable devices, saliva and blood sample analysis will be stored on the Atom5™ platform to ensure one single-sign on portal for all study staff and participants. The type and level of data access granted will be in accordance with the staff member's role (view only vs data entry and editing rights). Access to Atom5™ will be via entry of a username (Global ID) and password. Access to the system by a user will be logged with a date and time stamp for audit purposes. Data will be stored on an Azure Microsoft Cloud in the UK (Cardiff). Data export will be conducted in CSV files at several time points during the study to the research team to enable data checking and interim as well as final study analyses. Anonymised data will be stored on a secure server within UoB for a period of 10 years. For those participants who have consented to be contacted for future ethically approved research their data will be stored in a secure database for 10 years after study completion. All Participant Identifiable Data (PID) stored on the Atom5™ platform will be deleted at the time of decommissioning and all data transferred to the study sponsor.

### **9.5.2 Co-Production**

Audio files will be transferred from the audio recorder into an encrypted folder on to the secure university server as soon as possible after the interviews. The recordings on the digital audio recorder will be deleted as soon as successful transfers to the encrypted laptop have been confirmed. The audio files will be securely shared with an approved transcription service authorised by the University of Birmingham. Only anonymised quotes from the transcript will be used in any arising publications or reports.

## **10.0 Data Analysis Plan**

### **10.1 Long COVID symptom clusters**

Unsupervised exploratory clustering techniques will be employed to identify distinct Long COVID symptom clusters (objective 4).

We will first perform dimension reduction using one of: multi-dimensional scaling (MDS), t-stochastic neighbour embedding (t-SNE) and uniform manifold approximation and projection (UMAP). This first step will reduce dimensionality of the global data set while retaining local distances between individuals.

Following the dimensionality reduction step, we will employ clustering algorithms that have been shown to work well in medical settings:

- (1) k-means clustering, which locates the stable set of centroids of a predetermined number of k clusters.
- (2) Fuzzy c-means cluster analysis, a version of k-means clustering which allows data points to have partial cluster membership.

(3) Hierarchical agglomerative clustering, which joins observations in a recursive fashion satisfying some linkage criterion until  $k$  clusters have been generated. We will use the Ward linkage, which joins observations that minimise the variance of merged clusters.

(4) Gaussian finite mixture models, a model-based approach to clustering which associate each data point with a multivariate (ellipsoidal) Gaussian distribution.

(5) DBSCAN/HDBSCAN, algorithms, which identify clusters of dense observations among unassigned lower-density observations.

The optimal number of clusters for all methods (except DBSCAN) will be determined using model selection methods and internal cross validation. Cluster membership goodness of fit will be evaluated by: (1) the Jaccard similarities (intersection size divided by union size) of the original clusters to the most similar clusters in the resampled data, and (2) the average silhouette score, where the silhouette score varies between +1 for an observation aligned with its cluster centre and -1 for an observation aligned with the centre of another cluster. We will determine mean bootstrapped Jaccard and silhouette indices to assess cluster stability. The plot of within-groups sum of squares vs  $K$  will be checked graphically for optimal  $K$  (elbow method) and a minimum BIC.

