**Data-driven analysis to identify distinct Long COVID syndromes (Objective 4, part A)**

We will define distinct symptom clusters (syndromes) using linked data from CPRD and Atom5™ platforms. We will employ clustering algorithms that have been shown to work well in medical settings, with binary and mixed variables: (1) complete linkage hierarchical clustering; (2) probabilistic c-means cluster analysis; (3) density peaked clustering analysis. We will evaluate algorithm performance and the optimal number of clusters (e.g. by internal validation against a holdout dataset using metrics such as Gap statistic and silhouette index).

We will describe the epidemiology of patients within each Long COVID syndrome as well as health service use (primary care consultations, prescriptions, A&E attendances and hospital admissions) and mortality risk and compare these to both sets of matched control patients. We will identify whether Long COVID syndromes are

associated with particular population groups such as BAME groups, patients with long-term conditions, and other vulnerable population groups identified by Public Health England.

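### Section 10.1 embeds the whole data set before resampling and does not say the embedding is repeated; followed in that order, bootstrapped Jaccard and silhouette overstate cluster stability

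*Protocol*

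**What the plan says.** Protocol section 10.1 describes a sequence. Dimension reduction comes first, by one of MDS, t-SNE or UMAP, and its purpose is given as: "This first step will reduce dimensionality of the global data set while retaining local distances between individuals". The next step is introduced with "Following the dimensionality reduction step, we will employ clustering algorithms that have been shown to work well in medical settings", followed by five families: k-means, fuzzy c-means, Ward hierarchical clustering, Gaussian mixtures and DBSCAN/HDBSCAN. On the number of clusters: "The optimal number of clusters for all methods (except DBSCAN) will be determined using model selection methods and internal cross validation". Fit of cluster membership is judged by "the Jaccard similarities (intersection size divided by union size) of the original clusters to the most similar clusters in the resampled data" and by the average silhouette score. The section then says: "We will determine mean bootstrapped Jaccard and silhouette indices to assess cluster stability". It gives no Jaccard threshold and does not say whether the embedding is refitted within resamples or folds.

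A holdout appears elsewhere, in the WP2 part of section 5.0 (Objective 4, part A). There it is an example of how performance might be evaluated: "by internal validation against a holdout dataset using metrics such as Gap statistic and silhouette index". That passage lists different algorithms and has no dimension reduction step.

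**The concern.** In MDS, t-SNE and UMAP a person's coordinates depend on everyone else in the fit. If the map is made once from the full cohort and people are then resampled with their coordinates unchanged, each resample inherits the same map. The bootstrap asks whether k-means or Ward splits that map the same way again. It does not ask whether another sample of patients would give a similar map and similar groups, which is what a reader takes cluster stability to mean. Cross validation for K has the same weakness, because the people left out have already shaped the coordinates.

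The clusters matter downstream. They define the syndromes for BioWear sampling (section 6.5.3), for the comparison of epidemiology and health service use, and for the mapping of therapies (section 5.0). An inflated stability figure would lend these steps more confidence than the data justify.

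**Working it through.** **Plan's own figure.** The protocol states no Jaccard value or threshold, so there is nothing to reproduce. The check compares two ways of carrying out section 10.1.

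**Inputs from the protocol.** Cohort size 500 and K = 4, the lower end of the 4 to 6 range (section 14.1); MDS and t-SNE as two of the three named reductions; k-means as one of the named algorithms; bootstrapped Jaccard as the stability index (all section 10.1).

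**Assumed inputs, not in the protocol.** 40 binary symptoms; two-dimensional embedding; t-SNE perplexity 30; 20 bootstrap samples per data set; 4 data sets per scenario. The severity scenario has one continuous gradient and no groups. In the cluster scenarios each of four groups has 10 symptoms raised by 1.0 (weak) or 3.0 (strong) on the logit scale.

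**Formula.** For an original cluster A and a cluster B in the resample, J(A, B) = |A ∩ B| / |A ∪ B|. Take the largest J for each original cluster, then average over clusters and resamples. *Fixed*: embed once and re-cluster the resampled people's existing coordinates. *Refitted*: embed the resampled people afresh, then cluster.

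**Results.** Means over four data sets; the gap is fixed minus refitted, from the rounded means.

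| Scenario | MDS fixed | MDS refitted | Gap | t-SNE fixed | t-SNE refitted | Gap |
|---|---|---|---|---|---|---|
| Independent symptoms, no clusters | 0.77 | 0.33 | 0.44 | 0.71 | 0.21 | 0.50 |
| Severity gradient, no clusters | 0.84 | 0.68 | 0.16 | 0.78 | 0.43 | 0.35 |
| Four weak clusters | 0.72 | 0.44 | 0.28 | 0.72 | 0.22 | 0.50 |
| Four strong clusters | 0.92 | 0.75 | 0.17 | 1.00 | 0.96 | 0.04 |

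Example of a mean (MDS, independent symptoms): fixed (0.783 + 0.790 + 0.781 + 0.716)/4 = 0.77; refitted (0.316 + 0.321 + 0.336 + 0.338)/4 = 0.33.

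With a fixed map, data without any structure score 0.71-0.77, no lower than four weak but real clusters at 0.72. The index then cannot tell the two apart.

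**Checks on the result.**
- *Duplicates.* A bootstrap sample repeats people, which lowers refitted t-SNE values. With 80% subsamples drawn without replacement the direction was the same in every run. For independent symptoms: MDS 0.86-0.91 fixed versus 0.43-0.53 refitted; t-SNE 0.68-0.86 versus 0.21-0.22. The smallest gap was 0.905 − 0.885 = 0.02 (MDS, one severity data set).
- *Software.* One data set in each of three scenarios was rerun with a standard t-SNE library: severity 0.81 versus 0.52, weak clusters 0.76 versus 0.28, strong clusters 1.00 versus 0.98.
- *Other assumed data.* A run with 20 binary symptoms, MDS and k-means gave 0.73 versus 0.36 (no clusters), 0.76 versus 0.57 (moderate) and 0.90 versus 0.70 (strong). Another 20-symptom run with moderate groups gave 0.85 versus 0.37 for t-SNE at perplexity 30 and 0.77 versus 0.55 for MDS. Ward linkage went the same way, for example 0.63 versus 0.35.

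The simulations measure Jaccard. The argument for the bootstrapped silhouette and for cross validation of K is by the same reasoning and was not simulated.

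**The case against.** The strongest reply is that the protocol never says the coordinates are held fixed. Its Jaccard definition refers to clusters in resampled data, which is compatible with rerunning the whole pipeline; the word global may only be a contrast with local; and what sits inside a bootstrap loop is often left to a statistical analysis plan. This stands in part: a single fit is inferred from the order of steps and is not stated. But section 10.1 does not leave the order open. It puts the reduction of the whole data set first and everything else after it, and an analyst following that order would most naturally resample points on one map.

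Four stronger readings are tempting and lack support:

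- *The holdout check reuses the embedded coordinates.* Section 10.1 has no holdout. It appears in section 5.0 only as an example, with other algorithms and no dimension reduction. The problem arises only if the two descriptions are combined.
- *An inflated Jaccard would pass false syndromes into BioWear.* No Jaccard threshold is set. Sampling goes by the four most prevalent syndromes, the clustering is described as exploratory, and silhouette, BIC and the elbow plot are also used.
- *t-SNE must be confined to display.* The protocol commits to one of three methods, so t-SNE may not be used at all, and such a restriction would be a preference.
- *The simulated gaps predict this study's gap.* They rest on assumed binary symptoms, whereas the SBQ-LC uses five-point ordinal responses. UMAP and most of the listed algorithms were not tested.

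It is also fair to say that section 14.1 plans for well-separated clusters (effect size 4 or over), where the t-SNE gap nearly vanishes. The MDS gap does not (0.92 versus 0.75), and a stability check is most needed when good separation cannot be taken for granted.

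**Conclusion.** The point holds in conditional form. Section 10.1 places the embedding of the whole data set before clustering, cross validation and the bootstrap, and does not say that it is repeated. Carried out in that order, the stability indices omit the embedding's own sampling variability and are too favourable. On assumed data (n = 500, K = 4, two dimensions), mean Jaccard fixed versus refitted is about 0.7-0.8 versus 0.2-0.4 for independent symptoms without clusters. For strong clusters it is about 0.9 versus 0.7-0.75 with MDS and 1.00 versus 0.96 with t-SNE. The direction was consistent in every run; the size depends on the data and the method. If the analysts already intend to rerun the embedding in each resample, the point reduces to one missing sentence.

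**What to change.** Add to section 10.1 that dimension reduction and clustering, and the choice of K where it is being assessed, are rerun within every bootstrap sample or fold, and that the Jaccard and silhouette from this full-pipeline resampling are the reported stability figures. Because duplicates depress refitted t-SNE values, subsampling without replacement is a useful companion analysis. If the holdout of section 5.0 is to be used with this pipeline, separate it before the embedding is fitted and choose a reduction method that can place new people on the fitted map; standard t-SNE cannot.

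The cost is wording, more computing time and less favourable reported stability. Refitting does not by itself show that clusters exist: with MDS, a severity gradient without groups still scored 0.68 after refitting, above four weak real clusters at 0.44. The figure should therefore be reported as stability only.

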### **6.5.3 Bio-sampling and wearables (BioWear) sub-cohort**

Researchers will identify distinct symptom clusters (syndromes) using linked data from CPRD and data collected via the Atom5™ platform. A random sample of up to 300 participants (200 participants with Long COVID, with 50 sampled from each of the four most prevalent Long COVID syndromes, and 50 participants from each of the two control groups) who have previously consented to be contacted for bio-sampling will be identified and invited to take part in the BioWear sub-study. Selected participants will be sent an invitation to participate and the BioWear sub-study PIS via the Atom5™ app, SMS message or by post for those who have expressed having difficulty accessing digital platforms. Those individuals showing an interest in taking part will be contacted by a member of the research team to arrange a date and time for blood and saliva sample collection and to be provided with a wearable device (Garmin Vivosmart4).

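### Sections 5.0 and 10.1 specify different clustering procedures for objective 4, and clustering after t-SNE or UMAP, as 10.1 allows, could turn a pure severity continuum into stable-looking clusters

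*Protocol*

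**What the plan says.** Protocol section 5.0 (WP2, objective 4 part A) names three algorithms: "1) complete linkage hierarchical clustering; (2) probabilistic c-means cluster analysis; (3) density peaked clustering analysis". It mentions no embedding, and it evaluates performance and the number of clusters, for example, "by internal validation against a holdout dataset using metrics such as Gap statistic and silhouette index".

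Section 10.1, the data analysis plan for the same objective, starts with an embedding: "We will first perform dimension reduction using one of: multi-dimensional scaling (MDS), t-stochastic neighbour embedding (t-SNE) and uniform manifold approximation and projection (UMAP"). It then states: "Following the dimensionality reduction step, we will employ clustering algorithms that have been shown to work well in medical settings". The algorithms listed are k-means, fuzzy c-means, hierarchical agglomerative clustering ("We will use the Ward linkage, which joins observations that minimise the variance of merged clusters"), Gaussian mixtures and DBSCAN/HDBSCAN. On the number of clusters K: "The optimal number of clusters for all methods (except DBSCAN) will be determined using model selection methods and internal cross validation". An elbow plot and minimum BIC are added. Bootstrapped Jaccard and average silhouette judge fit and stability.

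The WP2 overview in 5.0 leaves open whether distinct phenotypes exist. Section 6.5.3 nevertheless plans the bio-sampling "with 50 sampled from each of the four most prevalent Long COVID syndromes", and 11.1 also assumes four syndromes.

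**The concern.** There are two problems.

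First, the protocol prescribes two procedures for one objective. An analyst could follow either and claim compliance.

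Second, 10.1 clusters embedded coordinates. Its stated reason for the embedding is that local distances are retained. Silhouette, Ward linkage and within-group sums of squares also use distances between groups, and density methods use density. t-SNE and UMAP preserve neither. Separation seen on their coordinates can therefore be created by the embedding. Because 10.1 gives no rule for choosing among the three embeddings, an unspecified choice can affect whether syndromes are found.

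The bio-sampling strata, the mapping of therapies to syndromes in WP3 and the co-produced intervention are all organised by these clusters. If patients differ only in overall severity, spurious clusters would misdirect that work.

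**Working it through.** **Step 1. The two sections side by side**

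| Element | Section 5.0 | Section 10.1 |
|---|---|---|
| Embedding before clustering | None mentioned | One of MDS, t-SNE, UMAP |
| Hierarchical linkage | Complete | Ward |
| Density method | Density peaks | DBSCAN/HDBSCAN |
| c-means | Probabilistic | Fuzzy (may be the same method) |
| k-means, Gaussian mixtures | Not listed | Listed |
| Evaluation | Holdout; Gap, silhouette (as examples) | Cross validation, bootstrap Jaccard, silhouette, elbow, BIC |

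Apart from c-means, every row differs; silhouette is the one shared index.

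**Step 2. The plan's own figure**

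Section 14.1 expects power above 80% with 500 patients for well-separated clusters (effect size 4) of at least 5% of the cohort, for K = 4 to 6. The smallest cluster is 0.05 × 500 = 25, inside the stated 20-30. The protocol gives no formula, so this was simulated with spherical normal clusters, centroids 4 SD apart and the smallest cluster at 5%.

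- Gaussian mixture with minimum BIC (25 runs per K) chose the true K in 100% of runs for K = 4, 5 and 6. The figure therefore reproduces if detection means finding the right K.
- k-means with silhouette (60 runs per K) chose the true K in 15%, 53% and 70%.

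The figure concerns power when clusters exist. It says nothing about what happens when there are none.

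**Step 3. No true clusters**

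Assumed data: n = 500 and 20 items. Item j for person i is x = 0.7·f + √(1 − 0.7²)·e, with one severity factor f, cut into five ordered levels. There were 12 data sets. Each was analysed as raw symptoms and after a two-dimensional classical MDS, t-SNE (perplexity 30) or UMAP (15 neighbours).

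- Silhouette for one person: (b − a)/max(a, b), where a is the mean distance to the person's own cluster and b to the nearest other cluster. It is undefined at K = 1, so K ran from 2 to 8.
- BIC and Gap started at K = 1. HDBSCAN used a minimum cluster size of 25.
- Jaccard: intersection divided by union, over 10 bootstrap resamples with the embedding held fixed and K forced to 4.

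Counts are out of 12; silhouette and Jaccard at K = 4 are means.

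| Input | K by silhouette | Silhouette, K=4 | HDBSCAN clusters | K by BIC | K by Gap | Jaccard, K=4 |
|---|---|---|---|---|---|---|
| Symptoms | 2 in 12 | 0.12 | 0 in 12 | not run | 4 in 9, 5 in 3 | 0.88 |
| MDS | 2 in 12 | 0.40 | 0 in 6, 2 in 6 | 1 in 2, 2 in 7, 3 in 3 | 1 in 11, 4 in 1 | 0.91 |
| t-SNE | 2 in 12 | 0.41 | 2 in 8, 3 in 4 | 3 in 10, 4 in 2 | 1 in 1, 3 in 2, 4 in 9 | 0.90 |
| UMAP | 2 in 12 | 0.48 | 2 in 7, 3 in 3, 4 in 2 | 3 in 6, 4 in 4, 5 in 2 | 1 in 10, 2 in 1, 5 in 1 | 0.93 |

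- HDBSCAN gave the correct null answer on the symptoms every time, and never after t-SNE or UMAP.
- BIC never chose K = 1 after t-SNE or UMAP.
- Silhouette at K = 4 rose after all three embeddings, MDS included, so part of the rise comes from projecting to two dimensions. What MDS kept was some ability of HDBSCAN, BIC and Gap to show one cluster or none.
- Jaccard was about 0.9 on every input.

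**Step 4. A second simulation**

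Six data sets of 500 people with 16 binary items and one severity factor were run through t-SNE and k-means at K = 4 to 6. Silhouette was 0.37-0.42 on the embedding and 0.05-0.10 for the same labels on the symptoms. Jaccard with the embedding held fixed was 0.70-0.92. Running t-SNE twice on the same data (two starting configurations) gave K = 4 memberships with an adjusted Rand index of only 0.51-0.68.

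**The case against.** A reader might go further and infer that the plan cannot return a no-cluster answer, or that it would report four to six syndromes whatever the data. The documents do not support either.

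- Minimum BIC can select K = 1, DBSCAN/HDBSCAN can leave everyone unassigned, and the Gap statistic in 5.0 is defined at K = 1. Each returned one or no cluster in some of the runs above. Only silhouette excludes K = 1 by construction.
- K = 4 to 6 appears only as a sample-size assumption in 14.1. With no true clusters, silhouette chose K = 2 every time.
- Multiplying three embeddings by five algorithms into 15 competing analyses misreads 10.1, which uses one embedding. The fair complaint is that the choice is not fixed.

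Other defences carry some weight. Section 5.0 is a design overview and 10.1 is the analysis plan. However, in 5.0 only the evaluation metrics are given as examples; the algorithm list is stated firmly. Section 10.1 does not say that silhouette is computed on the embedding or that the embedding is held fixed in resampling, and those were choices made in the simulations. Resampling the whole pipeline, which 10.1 permits, might expose the instability. High Jaccard is not caused by the embedding, since it was 0.88 on the raw symptoms. The work is labelled exploratory, 6.4.1 sets 200 as a maximum, and therapy recommendations also rest on rapid reviews and expert consensus. Acceptance cut-offs may stand in a statistical analysis plan not seen here, and this point does not rely on their absence.

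**Conclusion.** The point holds in two parts.

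The conflict between 5.0 and 10.1 is a matter of text and needs no assumption: linkage, density method, embedding, algorithm list and evaluation scheme differ for the same objective.

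The second part is a risk, not a certainty. If t-SNE or UMAP is the embedding chosen, a pure severity continuum could be reported as several clusters that look separated and stable. In the simulations that meant 2 to 4 by HDBSCAN and 3 to 5 by BIC. MDS is less affected on HDBSCAN, BIC and Gap, though not on silhouette. The frequencies rest on 12 data sets, one assumed loading, two dimensions and one set of tuning values, so they illustrate direction and plausibility only.

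This should be changed, because 5.0 itself asks whether distinct phenotypes exist and 10.1 as written can blur the answer.

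**What to change.** 1. Keep one method list for objective 4 and align 5.0 and 10.1 to it.
2. Cluster the symptom data directly with a method suited to binary and ordinal items (a suitable dissimilarity, or latent class analysis), and use t-SNE or UMAP for display only. If an embedding is kept, fix it in advance, compute silhouette on the original symptoms, and bootstrap the whole pipeline including the embedding.
3. Allow K = 1, and accept K > 1 only if the indices exceed those from data simulated under a single severity factor, for example their 95th percentile. Carrying the Gap statistic into 10.1 is not enough alone: on raw one-factor symptoms it chose K = 4 or 5 in 12 of 12.
4. State what happens to bio-sampling if fewer than four clusters, or none, are declared. Sections 6.5.3 and 11.1 assume four syndromes, whereas 6.4.1 takes 50 per cluster with 200 as a maximum; these need reconciling.

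The cost is protocol wording and computing time. The downside is that fewer or no clusters may be declared.
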